2.2.3 Exploratory Biological evaluations

Blood samples collected at baseline and at day 3 (+2d) post randomisation will be used for future biological assessments. Further information is provided in the GuARDS Biological Sampling Work Instruction.

3. STUDY DESIGN

3.1 Study Design

GuARDS is a UK multi-centre, parallel group, allocation concealed, open label, pragmatic, group sequential design randomised controlled trial, with internal pilot where the standard of care will be compared to standard of care with additional dexamethasone treatment. Interim analysis will be performed at set points in the trial (n=4, 50%, 65%, 80%, 100% of the sample size) which will allow for statistically controlled opportunities to stop for either overwhelming evidence of benefit (where dexamethasone works) or for ineffectiveness. Specifically, in PICO terms as an overview:

Population Adult patients with moderate to severe ARDS

Intervention: Intravenous Dexamethasone base 16.5mg (equivalent to Dexamethasone

Phosphate 20mg) and Dexamethasone base 8.25mg (equivalent to

Dexamethasone Phosphate 10mg)

Comparator Usual care²⁵

Outcome Primary outcome for clinical effectiveness is all-cause mortality 60 days after

randomisation.

3.2 Recruitment estimates

We plan to have 36 months of recruitment involving at least 60 sites and at 11/12th capacity (i.e., allow 1 month per 12 off for holidays, other reasons, etc.) gives 2145 centre months. This would result in the maximum sample size of 1708 participants (if the study continues at all interim analyses) being recruited over 2145 centre months = i.e., less than 1 per centre per month (0.8 on average).

3.3 Internal pilot stage

Our project includes an internal pilot stage. We expect a lead time of 6 months for first recruitment, to secure regulatory approvals and to set-up the first five sites. We expect to add the remaining sites at around 10 sites/month over the next 6 months from start of month 7. This internal pilot will run for the first nine months of recruitment (from month 7 to month 16) to assess feasibility and protocol fidelity, with the eventual duration driven by patient numbers. Formal commencement of the pilot stage will be defined as the date of the first recruitment. Thus, for the proposed duration of the internal pilot, we would have an expected recruitment of 268 participants (or around one sixth of the maximum sample size) with mature 60-day mortality primary outcome data to enable the proposed sample size re-estimation step.

We will use a traffic light system to guide internal pilot stage progression, as recommended in recent best practice¹⁹:

Green: Progress to main trial with review of screening logs and protocol and any barriers to

recruitment addressed

Amber: Progress to main trial with ongoing site set-up, review of screening logs and protocol

deviations, and protocol review where necessary

Red: Decision to progress to main trial made by the Trial Steering Committee and the

funder (NIHR-HTA programme)

The internal pilot will reported to the funder (NIHR-HTA) using their designated management system.

[figure not shown]
Table- 2: Detail of internal pilot phase conducted during the first 9 months of recruitment

	Red	Amber	Green
% Threshold	<60%	61-99%	100%
Recruitment rate/site/month	<0.4	<0.6	0.8
Number of sites opened	~40	41-59	~60
Total number of participants recruited	<120	<200	288

The main parameters of interest to guide the progress of the trial and inform the procedures to be used in its delivery, are recruitment rates. Participants enrolled in the pilot will be included in the analysis of the main study. If recruitment of 268 patients occurs as planned or quicker than anticipated, progression to the full trial will occur. There will no pause to trial recruitment between completion of internal pilot stage, as per standard RCT practices.

During the internal pilot, we will audit screening logs, recruitment, reasons for exclusion, and protocol compliance. We will also measure the completeness of the primary outcome, which we anticipate should be >95% and optimise the educational materials for use in the wider site recruitment and set-up. Data from recruited patients in the internal pilot phase will be assessed for representativeness, by comparing demographic, ethnic, and indices of deprivation features with corresponding reports from ICUs in England, Wales and Norther Ireland (ICNARC case-mix programme reports)¹⁷ and Scotland (SICSAG reports)¹⁸.

Figure-2. Trial Overview

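### The internal pilot's traffic-light table does not follow its own percentage row or the text, so the red/amber boundary is ambiguous for 120 to 172 recruits (120 to 160 if the target is 268)

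*Protocol*

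**What the plan says.** All the relevant text is in Protocol Section 3.3 (Internal pilot stage), including Table 2.

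- **Text target.** For the planned pilot, "we would have an expected recruitment of 268 participants (or around one sixth of the maximum sample size"). Later in the section: "If recruitment of 268 patients occurs as planned or quicker than anticipated, progression to the full trial will occur".
- **Percentage row of Table 2** (red, amber, green; the last figure is also a percentage): "Threshold <60% 61-99% 100".
- **Rate row:** "Recruitment rate/site/month <0.4 <0.6 0.8".
- **Sites row:** "Number of sites opened ~40 41-59 ~60".
- **Participants row:** "Total number of participants recruited <120 <200 288".
- **Actions.** Green and amber both progress to the main trial, amber with continued site set-up and review of screening logs and deviations. Red hands the decision to the Trial Steering Committee and the funder.
- **Timing.** The pilot covers the first nine months of recruitment, and the Table 2 caption repeats this, but the text adds "with the eventual duration driven by patient numbers".
- **Priority.** The text names recruitment rates as the main parameters of interest. It does not say what happens when two rows give different colours.

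**The concern.** A traffic-light rule works only if each possible pilot result maps to one colour. Here the percentage row and the numeric rows give different red limits, two numeric rows leave part of the range without a colour, and text and table name different targets.

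What is at stake is who decides. If the result is red, the Trial Steering Committee and the funder decide whether the trial goes on. If it is amber, the trial proceeds with a review. A poorly recruiting pilot could therefore be handled in either way, depending on which row is read. If this is settled only once the recruitment figures are known, the cut-points are no longer pre-specified.

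**Working it through.** **Inputs.** From Section 3.3: text target 268; green values 288 participants, 0.8 per site per month and about 60 sites; red limits 120, 0.4 and about 40; amber upper limits 200, 0.6 and 59; percentage bands under 60%, 61 to 99% and 100%. From Section 4.1: maximum sample size 1708.

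**Step 1: where 268 and 288 come from.** Both can be reproduced as site-months × 0.8, but the protocol gives no month-by-month schedule, so these ramps are assumptions fitted to the figures:
- 5+10+20+30+40+50+60+60+60 = 335 site-months; 335 × 0.8 = 268.
- 5+15+25+35+45+55+60+60+60 = 360 site-months; 360 × 0.8 = 288.

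The remark that the pilot is about one sixth of the maximum does not separate them: 268/1708 = 15.7%, 288/1708 = 16.9%, and 1708/6 = 285.

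**Step 2: cut-points against the percentage row.**

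| Row (100% value) | Red limit as % of 100% value | 60% would be | Top of amber as % of 100% value | No colour |
|---|---|---|---|---|
| Participants (288) | 120/288 = 41.7% | 172.8 | 199/288 = 69.1% | 200–287 |
| Participants (268) | 120/268 = 44.8% | 160.8 | 199/268 = 74.3% | 200–287, since the table's green is 288 |
| Rate (0.8) | 0.4/0.8 = 50% | 0.48 | 0.6/0.8 = 75% | 0.6 to under 0.8 |
| Sites (60) | 40/60 = 66.7% | 36 | 59/60 = 98.3% | none |

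The three red limits sit at about 42%, 50% and 67% of their own green values, so no single percentage describes them. Participants and rate are more lenient than the header; sites is stricter.

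**Step 3: the colour of the planned result.** A pilot that recruits 268 has no colour on the participants row, is amber on the percentage row if the target is 288 (268/288 = 93%), and progresses according to the text.

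**Step 4: the band in which the decision-maker is unclear.**
- Target 288: red by percentage below 173, red by count below 120. Counts of 120 to 172 conflict.
- Target 268: red by percentage below 161. Counts of 120 to 160 conflict.

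**Step 5: does the rate row resolve it?** On the assumed 335 site-months, 0.4 × 335 = 134, so counts below 134 are also red by rate. For example, 120/335 = 0.36. The counts that are amber on both the participants and rate rows but red by the header are then 134 to 160, which is 50 to 60% of 268.

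If sites open slowly, the rate row no longer catches a pilot under half of target. With an assumed ramp of 5+10+20+30+40+41+41+41+41 = 269 site-months, 120 recruits give 120/269 = 0.45 per site per month with 41 sites open. The participants, rate and sites rows are all amber; only the percentage row (42 to 45%) is red.

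**The case against.** The strongest reply is that the table is a guide and that its defects seldom change a decision. Much of this stands.

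- **The uncoloured band.** Amber and green both progress, so the missing colour for 200 to 287 recruits cannot change who decides, and the text settles 268 directly. A reader might infer that the planned result fails the rule. It does not; what stays open is whether the amber or the green actions apply.
- **Under half of target passing as amber.** This is tempting from the participants row alone. If sites open on the assumed 335 site-month schedule, such a pilot is red on the rate row, which the text treats as the main parameter. The stronger reading needs slow site opening as well.
- **The only go/no-go rule.** The protocol also has futility bounds at three interim analyses (Sections 10.1.3 and 10.3) and a right to terminate at any time (Section 14.6). Amber requires review, and the pilot is reported to the funder whatever its colour.
- **A participant criterion that cannot fail.** The phrase about duration might suggest that the pilot runs until its target is met. The Table 2 caption fixes the first nine months, so this reading is not supported.
- **Projecting a weak pilot to the full trial.** Any statement that such a pilot could not reach the first interim analysis rests on an assumed ramp and a flat rate, neither of which the protocol gives.

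The reply does not remove the conflict at the red/amber boundary. There the colour does change who decides. Treating rates as the main parameter does not settle it either, because the rate row's own red limit is 50% and not 60%.

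**Conclusion.** The inconsistency is real and can be seen within Section 3.3 alone. Its practical effect is confined to the red/amber boundary: 120 to 172 recruits against a target of 288, or 120 to 160 against 268, are amber by count and red by percentage. If sites open on the assumed schedule and the rate row is applied as well, the unresolved range for a target of 268 narrows to about 134 to 160. The wider ranges need no assumption beyond the choice of target; the narrower one depends on the 335 site-month ramp, which is not in the protocol.

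This is a matter of feasibility governance. The primary analysis, type I error and the inclusion of pilot participants in the main analysis are unaffected. It should be corrected before the pilot is assessed, but it does not rank with faults that threaten the trial's conclusions.

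**What to change.** 1. Choose one pilot target, 268 or 288, and use it in both the text and Table 2.
2. Derive contiguous bands from the stated percentages:
   - Participants, target 268: red below 161, amber 161 to 267, green 268 or more.
   - Participants, target 288: red below 173, amber 173 to 287, green 288 or more.
   - Rate: red below 0.48, amber 0.48 to 0.79, green 0.80 or more.
   - Sites: red below 36, amber 36 to 59, green 60 or more.

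   If the present counts are what was intended, change the percentages instead. Each row then needs its own percentage, and the amber bands still have to be extended up to green.
3. State which row governs when rows disagree. Since the text already gives recruitment rates priority, the rate row is a natural choice, but any stated rule would do.
4. Assess at the nine months given in the Table 2 caption, and reword the phrase about duration to agree with it.

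The cost is one table and a few sentences in an amendment. The red limits for participants and rate become stricter, so the Trial Steering Committee and funder would be called on more readily. The red limit for sites becomes looser, moving from about 40 to below 36, and the sponsor should confirm that this is acceptable.

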4. STUDY POPULATION

Adult patients with ARDS, and moderate to severe hypoxaemia.

4.1 NUMBER OF PARTICIPANTS

A maximum of 1708 participants will be randomised 1:1 dexamethasone plus standard care vs, standard of care alone (around 854 per group).

4.2 INCLUSION CRITERIA

- (a) Provision of informed consent
- (b) Aged 16 years or older
- (c) Admitted to intensive care unit or high dependency unit (ICU)
- (d) Receiving respiratory support via invasive mechanical ventilation or non-invasive ventilatory support (non-invasive ventilatory support includes mask or helmet) or high flow nasal cannula (HFNC) >30L/min
- (e) Within 72 hours of diagnosis of ARDS with moderate to severe hypoxaemia defined as
 - i) a known acute clinical insult or new or worsening respiratory dysfunction (*Note: this includes new deterioration at any time-point during the ICU stay*), and
 - *ii*) opacities on chest imaging not fully explained by effusions, lobar/lung collapse/atelectasis, or nodules, and
 - iii) respiratory failure not fully explained by cardiac failure or fluid overload, and
 - iv) assessment of hypoxaemia done with either PaO₂/FiO₂ ratio <26.7 kPa from arterial blood gases, or SpO₂/FiO₂ <235 with SaO₂<97%

4.2.1 Additional notes on inclusion criteria listed in Section 4.2

- Provision of informed consent is only required for randomisation; it is not required for including patients in the screening log for the purposes of the CONSORT diagram. The rationale we need the number of patients fulfilling the inclusion criteria.
- Patients who change from mild hypoxaemia to moderate or severe hypoxaemia are eligible.
- For this trial, patients with unilateral opacities are eligible, as they would meet the definition of acute hypoxemic respiratory failure, and often have biological changes similar to ARDS. Furthermore, it is well recognised that there are differences in interpretation of chest radiography between observers (low inter observer agreement, validity, and reliability), what may appear to be a unilateral infiltrate on chest radiograph can seem bilateral infiltrates in a CT scan; and in mechanically ventilated patients radiological infiltrates can be masked in portable chest radiographs for numerous reasons²⁶⁻³⁰.
- We will include patients requiring other immunosuppressive drugs, provided there exists clinician equipoise for randomising such a patient.

4.3 EXCLUSION CRITERIA

- (a) ARDS due to microbiologically confirmed SARS-Co-V2 infection (COVID-19 ARDS)
- (b) Major upper gastrointestinal bleeding during current hospital admission, defined as requiring endoscopy and transfusion for two or more units of packed red blood cells. This exclusion criterion will exclude patients with contraindications to the glucocorticoids on the grounds of safety.
- (c) High dose glucocorticoids are required for a separate proven clinical indication at the time of randomisation as withholding treatments that have been deemed clinically effective, would be unethical.

Note: Low dose glucocorticoid treatments for clinical indications (defined as maximum daily dose of 200mg hydrocortisone or equivalent other steroids) is not an exclusion criterion.

- (d) Known hypersensitivity to dexamethasone³¹
- (e) Infections that are not being effectively treated as determined by the treating medical team
 - **Note:** Once infections are considered as effectively treated by the treating medical team, they are eligible for the trial.
- (f) Planned intensive care treatment withdrawal within next 24 hours as determined by the treating medical team
- (g) Patients who are known to be pregnant
- (h) Previous enrolment in the GuARDS trial

4.3.1 Explanatory notes on exclusion criteria listed in Section 4.3

Exclusion criterion (a) will exclude patients with COVID-19 who should be receiving glucocorticoids as part of their standard of care. There may be occasions where the reporting of COVID-19 status may be delayed and or proven clinical indications may become apparent few days after randomisation. This is likely to be a small proportion of patients. In this scenario, we will analyse on the intention to treat principles and provide additional sensitivity analyses, as appropriate.

Exclusion criterion (c): In patients receiving low dose (defined as maximum daily dose of 200mg hydrocortisone or equivalent other glucocorticoids) for clinical indications, the decision to continue this low dose glucocorticoids post randomisation in the usual care arm, and in the intervention arm will be at the discretion of the treating physicians.

Exclusion criterion (g) will exclude patients who are pregnant, as administering glucocorticoids in the first trimester of pregnancy increases the risk of cleft palate in the foetus, and in the third trimester of pregnancy, glucocorticoids are part of usual care for facilitating lung maturation in the foetus. Pregnancy tests are carried out on female patients on admission either to the emergency department, or to the hospital or when they are admitted to the ICU. This means that pregnant patients will be identified, and excluded appropriately. The SPC states that drug may pass to breast milk but no additional data is available. Lactation is not considered as an exclusion criterion as breastfeeding is highly unlikely in patients with moderate to severe ARDS in the ICU setting.

4.4 CO-ENROLMENT

Co-enrolment will be undertaken in line with the Sponsor co-enrolment policy (POL008). The CI, or delegate, and Co-sponsor Representative will complete the co-enrolment checklist (POL008-F01) where patients are already taking part in a Clinical Trial of Investigational Medicinal Product (CTIMP). Co-enrolment will also be permitted with studies investigating medical devices and non-interventional research studies on a case-by-case basis. Networks available to the CI and others will identify other studies involving ARDS patients and approaches to co-enrolment can be standardised with co-enrolment agreements where suitable.

5. PARTICIPANT SELECTION AND ENROLMENT

5.1 IDENTIFYING PARTICIPANTS

Participants will be identified by clinical ICU teams in collaboration with research teams using regular screening of patients, as often as feasible, from the time of ICU admission.

5.2 CONSENTING PARTICIPANTS

Many patients will lack mental capacity to consent at the time of screening and enrolment as a result of critical illness and the effects of sedative drugs. The legal frameworks that govern the inclusion of adults with incapacity in research in the UK are the Medicines for Human Use (Clinical Trials) Regulations, Adults with Incapacity (Scotland) Act, and Mental Capacity Act (England, Wales and Northern Ireland).

Where a patient lacks the capacity to consent, the law allows a legal representative to give consent for the patient to participate. Those who are able to act as a legal representative in Clinical Trials of Investigational Medicinal Products (CTIMPs):

- **Personal legal representative (PerLR)** i.e. Adult's Welfare Guardian or Welfare Attorney, or if not appointed: The adult's nearest relative, if neither are reasonably contactable.
- **Professional legal representative (ProLR)** i.e. A doctor responsible for the medical treatment of the adult if they are independent of the study, or a person nominated by the healthcare provider.

In GuARDS we will seek consent from the patient if they have capacity. Where a patient does not have capacity to consent, we will seek written consent from a legal representative (defined above).

5.2.1 Informed Consent

All patients who are potentially eligible for the trial will be critically ill, and often receive medications that could affect informed decision making, such as sedative drugs intermittently or by continuous infusion. They will therefore lack mental capacity. The Investigator is responsible for ensuring agreed consent procedures are followed before any protocol specific procedures are carried out.

5.2.2 Consent process

In clinical trials that include patients with diminished capacity requiring treatment in a critical care environment, a common approach is to seek consent from a legal representative and once the participant has regained capacity, to seek retrospective informed consent. For this trial, the greatest benefit of dexamethasone treatment is anticipated in the initial 72h post development of moderate/severe ARDS whilst patients will be receiving a range of care measures. Broadly, for consent, patients will fit into two categories:

- I. Some patients receiving non-invasive respiratory support (oxygen via HFNC or non-invasive ventilation) who may have capacity and can consent for themselves.
- II. For all other patients, we will require someone to consent on their behalf (i.e., legal representative)

In ICUs, research teams are integrated into clinical teams and/or work closely with them. Once the clinical and/or research teams have identified a patient is eligible for enrolment in the trial, the aim is to randomise the patient and start the allocated intervention as soon as possible. This will maximise the potential benefit from the intervention and ensure it is evaluated in the manner it would be used in routine care.

There will be four scenarios through which randomisation is likely to occur:

- a) Patient is able to provide consent.

 In this situation the patients will be consulted and provided with the Patient Information Sheet (PIS) sheet. After the opportunity to ask questions of the research team, patients who consent will be randomised.
- b) Patient's personal legal representative (PerLR) is present at the time eligibility occurs or attends within the next 48 hours.

In this situation the PerLR will be consulted and provided with the Patient Information Sheet (PIS) sheet. After the opportunity to ask questions of the research team, patients for whom consent is provided will be randomised. If the *PerLR* provides consent the patient will be randomised. From our collective experience of critical care trials, this is likely to be the default approach.

c) Patient's personal legal representative (PerLR) is not present at the time of eligibility or in the following 48 hours.

The patient's PerLR will be contacted via telephone. The PIS contents will be explained. They will be given the opportunity to ask questions by telephone before deciding whether to give oral consent which will be witnessed by an impartial (i.e. not on the delegation log) and recorded on the consent form. If the PerLR provides consent, the patient will be randomised. In-person consent will be obtained from the PerLR if they are present on site after the patient is randomised but still without capacity to consent. When the PerLR attends on site, they will be provided a copy of the PIS. Where the PerLR does not plan to attend site the witnessed oral consent will remain valid until the participant regains capacity. Attempts to contact the PerLR via phone will be recorded as part of the screening logs in the eCRF.

Note: As part of usual clinical practice, please ensure that the PerLR is aware that the patient was admitted to ICU before seeking consent for research.

d) Patient's personal legal representative (PerLR) is not present at the time eligibility occurs and either does not attend within 48 hours of fulfilling eligibility criteria, or cannot be contacted via phone after 3 attempts, but a professional legal representative (ProfLR) is identified who is immediately available.

In this situation, the ProfLR will be consulted. If the ProfLR provides consent the patient will be randomised. Retrospective consent will be obtained from the PerLR if they are present in the time from ProfLR consent and prior to the patient providing consent.

A flow diagram of the consent process is in Appendix 1.

5.2.3 Obtaining consent from participants who regain capacity.

Once a patient is deemed to have regained capacity, they will be approached by an authorised member of the site research team for informed consent to continue in the trial. This will be done as soon as practically possible.

Approach for informed consent from participants who regain capacity:

- The majority of enrolled participants will have their invasive mechanical ventilation discontinued through removal of the endotracheal tube, prior to them having demonstrated capacity and will therefore only be approached for informed consent following extubation, and sedation cessation. Of note, a minority of enrolled patients will have an endotracheal tube in place yet still be able to demonstrate capacity and be approached for informed consent prior to extubation, and sedation cessation.
- A small proportion of enrolled patients (estimated to be <10%) will have a tracheostomy performed as part of their routine clinical care and may be able to demonstrate capacity and be approached for informed consent at a time point when they are still receiving respiratory support.
- In the rare event that a patient was not approached for consent to remain in the trial prior to either ICU discharge and/or hospital discharge, the local research team will seek written consent at 60-day follow-up by sending a PIS and consent form. This will not be

considered a protocol deviation. The patient will be asked to return the signed consent form if they wish to remain in the trial, or contact the study team if they wish to be withdrawn. If the patient *neither* returns the signed consent form *nor* ask to be withdrawn from the trial, the ProfLR and/or PerLR consent will remain valid, and the patient will remain in the trial.

Process for informed consent from participants who regain capacity.

A Participant Information Sheet (PIS) will be provided to the patient by an authorised staff member who has received training in GuARDs Trial processes and procedures and in Good Clinical Practice (GCP). The PIS will provide information about the purpose of the study, what participation means for the patient (e.g. follow-up questionnaires at 60, 90 and 180 days), confidentiality and data security, and the future availability of the trial results. Patients will be given the opportunity to ask any questions they may have about participation in the GuARDs Trial. This process will be done in such a way to mitigate any potential undue influence or coercion. No therapeutic promises will be made.

After verifying that the PIS and Consent Form are understood, the person seeking consent will invite the patient to sign the Consent Form and will then add their own name and countersign it. A copy will be given to the patient, a copy placed in the patient's medical notes and the original kept in the Investigator Site File. If the patient is unable to physically sign the Consent Form (e.g. due to weakness, reduced dexterity), an independent witness can sign on their behalf.

If a patient does not wish to continue in the trial the options for withdrawal are detailed in Section 5.6 and should be recorded in the eCRF. Data collected up to the point of withdrawal will be retained.

